4.9.1.4 Deaths

Listing of all deaths will be provided.

4.9.1.5 Adverse Events of Special Interest

Definition of AESI is referred to the Protocol section 8.1.1.

Below AESIs will be summarized in both TEAE and post-dose AE:

- AESIs by PT
- AESIs by SOC and PT
- AESIs by SOC, PT and maximum CTCAE grade

Listings of AESIs will be provided.

4.9.2 Laboratory Data

Laboratory data for hematology, chemistry, and coagulation will be summarized for the actual values and the change from baseline value at each scheduled assessment. In addition, all data will be graded according to the NCI CTCAE Version 4.0, and summarized by baseline and maximum post-baseline CTCAE grade, including unscheduled visits. Shift tables will summarize the shift from baseline grade to maximum post-baseline CTCAE grade.

Listings of laboratory data for hematology, chemistry, and coagulation will be provided. In addition, listings of urinalysis, thyroid function testing, influenza testing, SARS-CoV-2 testing, and any microbiological tests performed will also be provided.

4.9.3 Electrocardiogram

Electrocardiogram (ECG) data will be summarized for the actual values and the change from baseline value at each scheduled assessment. Shift tables will summarize the shift from baseline to End of Treatment and worst post-baseline visit in ECG interpretation (categorized as normal; abnormal, not clinically significant; and abnormal, clinically significant).

Corrected QT interval by Fredericia (QTcF) will be summarized by categories as follows:

- QTcF interval > 450 ms
- QTcF interval > 480 ms
- QTcF interval > 500 ms
- QTcF interval increases from baseline > 30 ms
- QTcF interval increases from baseline > 60 ms

Listings of ECG data will be provided from both local and central reads of the data.

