7.4.7 ECG

Three consecutive (also called triplicate) 12-lead ECGs will be performed at defined timepoints throughout the study as per SoE (Table 1 and Table 2). Refer to Table 6 for the detailed schedule of ECGs, for patients treated with camidanlumab tesirine as monotherapy.

Refer to Table 7 for the detailed schedule of ECGs, for patients treated with camidanlumab tesirine in combination with pembrolizumab.

ECGs will be performed after the patient has rested for at least 5 minutes.

At timepoints coinciding with blood sample collection, including PK, ECGs should be taken prior to blood collection, and, when applicable, before vital signs measurements (example in Figure 2).

If a patient experiences Torsade de Pointes, additional concomitant PK samples (i.e., unscheduled) should be collected.

Table 6. Schedule for Triplicate ECG Collection (Q3W Schedule): Camidanlumab Tesirine as Monotherapy

Cycle	Day	ECG timepoint (window)
Screening	-	Any time within 21 days prior to C1D1
C1	D1	Pre-dose (preferably within 2 h prior to start of infusion) EOI (within 10 min prior to EOI) Post-dose* 4 h (\pm 15 min)
	D3	Post-dose* 48 h (\pm 24 h; but within 30 min prior to PK sample)
	D8	Post-dose* 168 h (\pm 48 h; but within 30 min prior to PK sample)
	D15	Post-dose* 336 h (\pm 48 h; but within 30 min prior to PK sample)
C2	D1	Pre-dose (within 30 min prior to PK sample) EOI (within 10 min prior to EOI) Post-dose* 4 h (\pm 15 min)
	D3	Post-dose* 48 h (\pm 24 h; but within 30 min prior to PK sample)
	D8	Post-dose* 168 h (\pm 48 h; but within 30 min prior to PK sample)
	D15	Post-dose* 336 h (\pm 48 h; but within 30 min prior to PK sample)
C3 and C4	D1	Pre-dose (within 30 min prior to PK sample) Post-dose* 4 h (\pm 15 min)
C5, C7 every other cycle	D1	Pre-dose (within 30 min prior to PK sample)
EOT		Any time (but within 30 min prior to PK sample)
Unscheduled		Any time

Abbreviations: C=cycle; D=day; ECG=electrocardiogram; EOI=end of infusion; EOT=end of treatment; h=hour; min=minutes; PK=pharmacokinetics; Q3W=every 3 weeks.

* Post-dose timepoint is counted from start of infusion.

Table 7. Schedule for Triplicate ECG Collection (Q3W Schedule): Camidanlumab Tesirine in combination with Pembrolizumab

Cycle	Day	ECG timepoint (window)
Screening	-	Any time within 21 days prior to C1D1
C1	D1	Pre-dose (preferably within 2 h prior to start of infusion) EOI (within 10 min prior to EOI of camidanlumab tesirine) Post-dose* 4 h (\pm 15 min)

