C2	D1	Pre-dose (preferably within 2 h prior to start of infusion) EOI (within 10 min prior to EOI camidanlumab tesirine) Post-dose* 4 h (\pm 15 min)
C3, C5, every other Cycle	D1	Pre-dose (preferably within 2 h prior to start of infusion)
EOT		Any time (but within 30 min prior to PK sample)
Unscheduled		Any time

Abbreviations: C=cycle; D=day; ECG=electrocardiogram; EOI=end of infusion; EOT=end of treatment; h=hour; min=minutes; PK=pharmacokinetics; Q3W=every 3 weeks.

* Post-dose timepoint is counted from start of infusion of camidanlumab tesirine

Electrocardiograms will be submitted for a central review; however, local ECG results may be used for patient eligibility or medical decisions when central results are not received in a timely manner.

Submission instructions for the central review will be provided in a separate manual. Assessments will include determination of heart rate and rhythm and the PR, QRS, QT, QTcF, and QTcB intervals.

[figure not shown]

Figure 2. Preferred Sequence for Triplicate ECG, Vital Signs, and PK Sample Assessments at End of Infusion (EOI)

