9.8.3 Additional Safety Assessments

The results of scheduled assessments of vital signs, physical examinations, ECOG performance status, and 12-lead ECGs will be summarized. All data will be reported according to the nominal visit date for which it was recorded (i.e., no visit windows will be applied). Unscheduled data will be included in “worst case” summaries, which will capture a worst case across all scheduled and unscheduled visits after the first dose of study drug. All data will be listed. Further details will be provided in the SAP.

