3.3 Modifications to the statistical section of the protocol

Not applicable.

4 Statistical methods

No hypothesis testing will be performed in this study.

All analyses will use SAS® version 9.4 or higher.

Unless otherwise stated, tables, listings, and figures will be broken down by monotherapy and combination therapy and then by dose level in dose-escalation part, and by group in dose-expansion part. Additional tables broken down by indication and by indication at recommended dose for expansion (RDE) will be specified in later sections. All data will be provided in listings. Tables and figures are based on the defined analysis population.

Categorical data will be presented using counts and percentages, with the number of patients in the analysis population as the denominator for percentages. Percentages will be rounded to 1 decimal place and not be displayed for zero counts.

Continuous data will be summarized using the number of observations (n), mean, standard deviation (std), median, minimum, and maximum. Minima and maxima will be rounded to the precision of the original value, and means, medians, and 95% confidence intervals (CIs) if presented will be rounded to 1 decimal place greater than the precision of the original value. The std will be rounded to 2 decimal places greater than the precision of the original value, up to a maximum of 3 decimal places.

CI will be two-sided and use $\alpha=0.05$ (i.e., 95% CIs), unless otherwise specified. For exact estimates, the CI will be calculated using the Clopper–Pearson exact method. For Kaplan–Meier estimates, the CI will be calculated using the Greenwood's formula with (complementary) log-log transformation.

Kaplan–Meier plots will be provided along with Kaplan–Meier estimates.

The Baseline value is defined as the last non-missing value or measurement taken prior to the first dose of study drug.

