6.1.2 Unscheduled visits

Unscheduled visit measurements of laboratory data, vital signs, and ECG will be used for computation of baseline and worst values and/or grades. Re-windowing for unscheduled visits will not be performed.

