6.1.3 Duplicated visits

Depending on the statistical analysis method, single values may be required for each analysis window. For example, change from baseline by visit usually requires a single value per visit. Unless otherwise noted throughout the rest of this document, when a single value is needed, the following rule(s) will be used:

- If more than 1 assessment occurs during the same nominal visit, select the record closest to the nominal day for that visit.
- If there are 2 assessments that are equidistant from the nominal day, the data of the assessment after the scheduled study day will be used.
- The last measurement will be used if multiple measurements are taken on the same day.

7 Reference List

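### SAP 4.9.3 has no rule for triplicate ECGs, so the general last-value defaults would rest each QTcF change on one tracing at each end

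*SAP*

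**What the plan says.** Protocol 7.4.7 sets the collection: "Three consecutive (also called triplicate) 12-lead ECGs will be performed at defined timepoints". On dosing days in Cycles 1 and 2 there are three such timepoints: pre-dose, end of infusion and 4 h. Table 7 gives the C2D1 one as "EOI (within 10 min prior to EOI camidanlumab tesirine"), so up to nine tracings can fall on one day. The ECGs go to central review, and "Submission instructions for the central review will be provided in a separate manual". Local results may stand in for eligibility or medical decisions when central results are late.

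The analysis rules are in the SAP:

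- SAP 4.9.3: "Electrocardiogram (ECG) data will be summarized for the actual values and the change from baseline value at each scheduled assessment". It then lists QTcF categories (>450, >480 and >500 ms; increases of >30 and >60 ms) and says both local and central reads will be listed. It does not mention replicates.
- SAP section 4: "The Baseline value is defined as the last non-missing value or measurement taken prior to the first dose of study drug".
- SAP 6.1.3, which applies wherever a single value is needed and nothing else is noted, with by-visit change from baseline as its example: "The last measurement will be used if multiple measurements are taken on the same day".
- SAP 6.1.2: "Unscheduled visit measurements of laboratory data, vital signs, and ECG will be used for computation of baseline and worst values and/or grades".

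Protocol 9.8.3 asks for worst-case ECG summaries "which will capture a worst case across all scheduled and unscheduled visits after the first dose of study drug" and leaves further detail to the SAP.

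**The concern.** A triplicate is taken so that short-term variation between tracings can be averaged out. The SAP's stated defaults do the opposite. The baseline rule picks the last tracing before dosing, and the same-day rule picks the last tracing afterwards. Two thirds of the collected tracings then play no part in the change from baseline.

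The defaults also stop short of the worst-case summaries. SAP 6.1.2 and Protocol 9.8.3 take a worst value across visits, but neither says whether the candidates are single tracings or one value per timepoint. The worst of many single tracings is higher than the worst of the corresponding means, even with no drug effect.

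Change from baseline in 12-lead ECG is a listed primary endpoint, and there is no control arm against which to judge a background rate of >30 ms increases. The reader of the clinical study report would take that rate at face value.

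**Working it through.** **Figure to reproduce.** None. The documents state no QTcF variability and no expected flag rate.

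**Inputs.** From the documents: three tracings per timepoint, the >30 ms category, and the Table 7 combination schedule. Post-baseline timepoints through C3D1 plus end of treatment are C1D1 EOI and 4 h; C2D1 pre-dose, EOI and 4 h; C3D1 pre-dose; and end of treatment, which makes 7. Assumed: no drug effect, normal errors, timepoint-to-timepoint SD t of 5 to 8 ms, and within-triplicate SD s of 5 to 10 ms.

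**Formulas.**

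- SD of one value: √(t² + s²) for a single tracing; √(t² + s²/3) for a mean of three.
- SD of change = √2 × SD of one value.
- False flag per comparison: P(Z > 30 / SD of change).
- Any flag over k timepoints sharing a baseline B: 1 − E_B[Φ((30 + B)/σ)^k], where σ is the SD of one value.

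**Worked case, t = s = 8.**

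- Single tracing: √(2 × (64 + 64)) = 16.0 ms; 30/16.0 = 1.875, so 3.0%.
- Triplicate mean: √(2 × (64 + 64/3)) = 13.1 ms; 30/13.06 = 2.30, so 1.1%.
- Any flag over the same 7 timepoints: 13.5% for single tracings, 5.5% for triplicate means.

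**Range, with the number of timepoints held at 7 for both rules.**

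| t / s (ms) | SD of change, single → mean | Per comparison | Any of 7 |
|---|---|---|---|
| 5 / 5 | 10.0 → 8.2 | 0.13% → 0.01% | 0.8% → 0.1% |
| 5 / 10 | 15.8 → 10.8 | 2.9% → 0.3% | 13.0% → 1.6% |
| 8 / 5 | 13.3 → 12.0 | 1.2% → 0.6% | 6.2% → 3.4% |
| 8 / 8 | 16.0 → 13.1 | 3.0% → 1.1% | 13.5% → 5.5% |
| 8 / 10 | 18.1 → 14.0 | 4.9% → 1.6% | 20% → 7.7% |

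Across these cases the SD of change falls by 10% to 32%. In a case just outside the range, where timepoint variation dominates (10/5), the any-of-7 rates are 13.0% and 9.8%. The gain is smaller but remains. False >60 ms flags per comparison stay below 0.05% under either rule.

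**Undefined unit for worst values.** If the worst single tracing at any of the 7 timepoints is compared with a last-tracing baseline, the rate at 8/8 is 22.8%. A simulation of 300,000 patients gives the same 22.8%, and 5.5% for triplicate means.

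**Monotherapy schedule.** Table 6 has 15 post-baseline timepoints through Cycle 4. A separate simulation (50,000 patients, 8/8) gives 9.3% for triplicate means, 21.0% for the last tracing at each timepoint and 32.2% for the worst tracing.

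**The case against.** The strongest reply is that the SAP does have a rule. SAP 6.1.3 governs wherever a single value is needed, and SAP section 4 fixes baseline. A reader might infer from the silence of 4.9.3 that the reduction is left entirely open and that programmers would derive different baselines. The documents do not support that: followed literally, they give one baseline and one by-visit value. What remains is that this default wastes the triplicate. In addition, 6.1.3 is headed as a rule for duplicated visits, so it may not have been written with planned replicates in mind.

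A reader might also infer that the same-day rule leaves only the 4 h ECG on C1D1 and C2D1. That reading is strained. SAP 4.9.3 promises summaries at each scheduled assessment, Tables 6 and 7 list pre-dose, EOI and 4 h separately, and 6.1.3 yields where the SAP says otherwise. The calculations above therefore keep all timepoints under both rules.

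On the source of the read, Protocol 7.4.7 gives local results only an operational role, which points to central reads for analysis. The SAP does not say so, but this is a confirmation to obtain and not a separate defect.

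Finally, the central-review manual is not among the documents. If the central value is already a triplicate mean and feeds the tables, the numerical effect is nil. This objection stands in full as a limit on the size. Nothing in the documents requires averaging, but it uses data already collected and is more precise than the stated default.

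**Conclusion.** The point holds as a minor one. SAP 4.9.3 lacks a replicate rule, and the defaults that fill the gap base each QTcF change on one tracing at each end. The unit for the categories and worst values is undefined.

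The mean change is unbiased either way; what suffers is precision and the false-flag rate. The size rests on assumed SDs, on no drug effect, and, for the any-timepoint figures, on the categories counting any post-baseline value, which 4.9.3 does not state. At 8/8 on the combination schedule the rate is 5.5% with triplicate means, 13.5% with single tracings and 22.8% with the worst tracing. For the roughly 30 Part 2 patients, the first two correspond to 30 × 0.055 = 1.7 and 30 × 0.135 = 4.1 false flags.

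No hypothesis test, dose-escalation rule or stopping rule uses these tables, and all ECG data are listed. A reader should not infer any effect on the trial's dose decisions.

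**What to change.** Add to SAP 4.9.3:

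- The analysis value is the mean of the available replicates at each nominal timepoint, with pre-dose, EOI and 4 h kept separate. It is used for actual values, change from baseline, all QTcF categories and the worst post-baseline QTcF value.
- ECG baseline is the mean of the last pre-dose triplicate.
- The same-day rule in SAP 6.1.3 does not apply to ECG replicates or to ECG timepoints on the same day.
- Central reads feed the tables (to be confirmed), with a note of whether the central value is already averaged.

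While that text is open, one clause could say whether the QTcF categories are per visit or any post-baseline.

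The cost is a few sentences and a simple derivation before database lock. No new data are needed and patient care does not change.

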- Changes from Baseline of safety laboratory values, vital signs, Eastern Cooperative Oncology Group (ECOG) performance status, and 12-lead electrocardiograms (ECGs) for patients treated with camidanlumab tesirine as monotherapy and for patients treated with camidanlumab tesirine in combination with pembrolizumab
- Frequency of dose interruptions and dose reductions for patients treated with camidanlumab tesirine as monotherapy and for patients treated with camidanlumab tesirine in combination with pembrolizumab
- Incidence of dose limiting toxicities (DLTs) (dose-escalation only) for patients treated with camidanlumab tesirine as monotherapy and for patients treated with camidanlumab tesirine in combination with pembrolizumab

Secondary Endpoints

- Overall response rate (ORR) according to Response Evaluation Criteria In Solid Tumors (RECIST) v1.1, for patients treated with camidanlumab tesirine as monotherapy and for patients treated with camidanlumab tesirine in combination with pembrolizumab
- Duration of response (DOR) defined as the time from the first documentation of tumor response to disease progression, as per RECIST v1.1, or death for patients treated with camidanlumab tesirine as monotherapy and for patients treated with camidanlumab tesirine in combination with pembrolizumab
- Progression-free survival (PFS) defined as the time between start of treatment and the first documentation of recurrence, progression, as per RECIST v1.1, or death for patients treated with camidanlumab tesirine as monotherapy and for patients treated with camidanlumab tesirine in combination with pembrolizumab

- Overall survival (OS) defined as the time between the start of treatment and death from any cause for patients treated with camidanlumab tesirine as monotherapy and for patients treated with camidanlumab tesirine in combination with pembrolizumab
- Concentrations and PK parameters of camidanlumab tesirine total antibody, PBD-conjugated antibody, and unconjugated warhead SG3199 in serum
- Frequency of confirmed positive anti-drug antibody (ADA) responses, their associated titers and, if applicable, neutralizing activity to camidanlumab tesirine after treatment with camidanlumab tesirine

Study Design:

This is a Phase 1b, multi-center, open-label study with a dose-escalation part and a dose-expansion part.

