 - replacement dose steroids in the setting of adrenal insufficiency
 - topical, inhaled, nasal, and ophthalmic steroids are allowed
21. Planned live vaccine within 30 days prior to the first dose of study treatment and during study treatment
22. Congenital long QT syndrome, or a corrected QTcF interval of ≥ 480 ms, at screening (unless secondary to pacemaker or bundle branch block).
23. Active second primary malignancy other than non-melanoma skin cancers, non-metastatic prostate cancer, *in situ* cervical cancer, ductal or lobular carcinoma *in situ* of the breast, or other malignancy that the Sponsor's medical monitor and Investigator agree and document should not be exclusionary.
24. Any other significant medical illness, abnormality, or condition that would, in the Investigator's judgment, make the patient inappropriate for study participation or put the patient at risk.
25. For patients treated with camidanlumab tesirine in combination with pembrolizumab: patients intolerant to checkpoint-inhibitor or with a history of the following \geq Grade 3 immune-related adverse events: hepatitis, renal, ocular, neurologic, cardiovascular, rheumatologic, and hematologic.
26. For patient treated with camidanlumab tesirine in combination with pembrolizumab: patients with a history of non-infectious pneumonitis related to prior systemic treatment and that require treatment with steroids within the last 6 months prior to enrolment.

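### The absolute QTcF rows in SAP 4.9.3 have no baseline condition or stated time base, so they mix prolongation present at entry with on-treatment change, mainly above 450 ms

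*SAP*

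**What the plan says.** SAP 4.9.3 announces the table with "Corrected QT interval by Fredericia (QTcF) will be summarized by categories as follows". The first row is "QTcF interval > 450 ms"; the other absolute rows use 480 and 500 ms. Change has its own rows, beginning with "QTcF interval increases from baseline > 30 ms" and followed by 60 ms. No absolute row is tied to the baseline value or crossed with a change row, and no time base is given.

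The same section plans actual values and change from baseline at each scheduled assessment. It also plans a shift table from baseline to end of treatment and to the worst post-baseline visit, but only for the overall ECG interpretation (normal, or abnormal with or without clinical significance).

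Protocol 5.2, criterion 22, excludes congenital long QT syndrome or a "corrected QTcF interval of ≥ 480 ms, at screening (unless secondary to pacemaker or bundle branch block"). SAP section 4 says: "The Baseline value is defined as the last non-missing value or measurement taken prior to the first dose of study drug". Protocol 9.8.3 plans worst-case ECG summaries that "capture a worst case across all scheduled and unscheduled visits after the first dose of study drug", and SAP 6.1.2 lets unscheduled ECGs enter both baseline and worst values. The protocol lists as a primary endpoint "Changes from Baseline of safety laboratory values, vital signs, Eastern Cooperative Oncology Group (ECOG) performance status, and 12-lead electrocardiograms (ECGs").

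**The concern.** The entry rule and the table cut-offs overlap. The 450 ms cut-off lies 30 ms inside the range that entry allows (480 − 450), and the 480 ms cut-off sits on the entry limit. Patients can therefore occupy an absolute row before their first dose, and the row does not separate them from patients who crossed the cut-off on treatment.

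This matters because there is no control arm to show the background rate, and tables are split by dose level. In a cohort of 3 to 6 patients, one patient is 33% (1/3) to 17% (1/6) of the row. A reader comparing the 450 ms row across dose levels or regimens could take a difference in who was enrolled for a difference in QT effect. The SAP already handles this problem elsewhere: laboratory grades (4.9.2) and ECOG status (4.9.5) get baseline-to-worst shift tables. QTcF category does not.

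**Working it through.** The documents give no expected rate for these rows, so there is no figure to reproduce.

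**Step 1: logic, no assumptions.**
- Baseline 451 to 479 ms, zero change: eligible, counted above 450 ms, absent from both change rows.
- Baseline 510 ms secondary to a pacemaker, zero change: eligible through the exception, counted in all three absolute rows.
- Eligibility uses the screening value but baseline is the last pre-dose value, so a baseline above 480 ms is also possible without the exception.

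**Step 2: single patient, no drug effect.** Take independent normal noise with SD s around a true value μ, and the worst of K post-dose time points: P(worst > T) = 1 − Φ((T − μ)/s)^K. Counting post-dose time points up to Cycle 4 Day 1 in Protocol Tables 6 and 7 gives K = 15 for monotherapy and K = 6 for the combination. The documents give no SD, so s = 6 to 12 ms is an assumption. The SAP has no rule for averaging the triplicate, which is one reason to keep the range wide.
- μ = 440, T = 450, s = 6: Φ(1.667) = 0.952, so 1 − 0.952^6 = 26% and 1 − 0.952^15 = 52%. With s = 12: Φ(0.833) = 0.798, giving 74% and 97%.
- μ = 455, T = 450: 99.8 to 100% as written. Also requiring baseline at or below 450 ms leaves 20 to 34% of all such patients; adding a rise above 30 ms leaves 0.1 to 21%.
- μ = 475, T = 480: 74 to 99.8% as written, 59 to 77% with the baseline condition, 0.1 to 25% with the rise as well.

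A baseline condition removes pre-existing prolongation but leaves much of the noise near a cut-off; the minimum rise removes most of that.

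**Step 3: whole population, no drug effect.** Simulation of 400,000 patients per setting. Assumptions: true QTcF normal with between-patient SD 20 ms; within-patient SD 6, 8 or 10 ms; screening value below 480 ms; 8 post-baseline ECGs. Percentages are of all patients.

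| Assumed mean (ms) | Worst value >450 | Baseline already >450 | New >450 and rise >30 |
|---|---|---|---|
| 410 | 6–11% | 3–4% | 0–1.5% |
| 420 | 14–22% | 7–9% | 0–2.8% |
| 430 | 28–38% | 16–18% | 0.1–4.2% |

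Across these settings, 28 to 55% of patients counted above 450 ms were already above it at baseline. Over 6 to 15 ECGs the rate above 480 ms is about 0.1 to 5%, and above 500 ms near zero. The pacemaker and bundle-branch-block exception is not modelled, because the documents do not say how many such patients to expect.

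Eight ECGs matches neither schedule. At mean 420 and SD 8, the rate above 450 ms is about 17% with 6 time points and 21% with 15, so the two regimens would differ slightly with no drug effect in either.

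**The case against.** The strongest reply is that the endpoint is change from baseline, and SAP 4.9.3 analyses change directly: by-visit change, the 30 and 60 ms rows, and a shift in overall interpretation. The patient who enters at 460 ms and stays there shows no change and appears in neither change row. That stands. A reader might infer from the overlap that the trial cannot tell whether the drug or the combination prolongs QTcF; the documents do not support this.

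A reader might also infer that the SAP reports pre-existing prolongation as a treatment effect. It does not: the rows are not called treatment-emergent or drug-related. If they were shown by visit with baseline alongside, entry values would be visible. The worst-value reading comes from Protocol 9.8.3, not from SAP 4.9.3. This narrows the point, but the silence on time base is itself a gap.

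Nor is any decision written in terms of these rows. No hypothesis is tested, and the dose-limiting toxicity definitions (Protocol 6.5), the stopping rules (4.3) and the steering committee's remit (4.1.3) do not refer to them. All data are listed, so in a small cohort each patient's baseline can be looked up. That also stands. The 17 to 33% share applies only to cohorts of 3 to 6: it is 10% in a dose level of 10, and 6 to 7% in the expansion groups (1/16 and 1/14).

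What survives is that no planned summary table shows whether a patient above a cut-off was already above it at baseline. The change rows do not, and the ECG shift table is not on QTcF.

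**Conclusion.** The point holds as a limit on how the absolute rows can be read. The overlap between entry rule and cut-offs follows from the text alone. It affects mainly the 450 ms row; the 480 and 500 ms rows are affected mainly through the pacemaker and bundle-branch-block exception. The no-effect rate of about 6 to 38% above 450 ms rests on assumed means of 410 to 430 ms, the assumed SDs, independent errors, 8 ECGs and the worst-value reading. The number of patients actually affected cannot be derived from the documents. Assessment of QTcF change, the primary endpoint, remains intact. This is a worthwhile, inexpensive improvement to a descriptive table.

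**What to change.** In SAP 4.9.3:

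1. State that the QTcF categories use the worst post-baseline value, consistent with Protocol 9.8.3.
2. Add a shift table from baseline category (≤450, >450–480, >480–500, >500 ms) to worst post-baseline category. Show new-onset counts for each threshold, with patients at or below it at baseline as denominator.
3. Add crossed rows for new values above 450 ms, and new values above 480 ms, each with an increase above 30 ms. These are needed because the baseline condition alone leaves much of the noise.
4. Flag pacemaker and bundle-branch-block patients.
5. Keep the absolute rows and the existing change rows.

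The cost is some SAP wording and one extra descriptive table from ECGs already scheduled. The drawback is small at-risk denominators in the dose-level cohorts, so counts should be shown beside percentages.
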